Topalian *et al.* found that high level of tumoral expression of PD-L1 was associated with higher response duration in nivolumab-treated patients [23]. But this was not observed in a nivolumab-ipilimumab study in melanoma [8]. Our preliminary work has shown that 15/20 NPC tumors (75%) expressed PD-L1, thus we plan to validate this marker in this study. The dynamic nature of tumoral PD-L1 expression may be dependent upon changes in the tumor microenvironment, and is closely correlated with the degree of immune infiltrate in tumors [32]. More recently in a phase 1b study of another PD-1 inhibitor, MK-3475 in recurrent head and neck squamous carcinoma, patients with tumors that overexpressed PD-L1 above an arbitrary cut-off point (Roche/Genentech assay used, defined as PD-L1 expression in $\geq 1\%$ of both tumor and adjacent immune cells) had higher tumor response rate (45.5%) than those who did not (11.4%) [33]. Based on these data, therefore, PD-L1 expression in the TILs in tumors will also be measured in this study. A recently published study has shown that the EBV oncogenic protein, latent membrane protein-1 (LMP-1) could up-regulate PD-L1 through STAT3, AP-1 and NF- κ B pathways in NPC cell lines. IFN- γ could also up-regulate PD-L1 independent of but synergistic with LMP1 in vitro [42].

Rationale for measuring absolute lymphocyte count

A study on ipilimumab has shown that an absolute lymphocyte count (ALC) of $> 1,000/\text{mL}$ and an increase in ALC around 2 months after treatment may predict clinical benefit [12]. But this was not observed in a nivolumab-ipilimumab study [8]. Further validation in this study is warranted.

Rationale for the functional MRI study

Discussed in section 9.2.2.1.

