13.1.3 Statistical Design Overview

A patient that has a confirmed response is considered a treatment “success”. The following one-stage design with an interim analysis requires a maximum of 35 evaluable patients, and simultaneously discriminates between tumor response rates of 5% vs. 20%.

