13.1.4 Final Analysis Decision Rule

Enroll 35 evaluable patients. If at least 4 patients have a confirmed tumor response (at least 11%) among the 35 evaluable patients, this agent would be considered worthy of further testing in this disease. If 3 or fewer patients have a confirmed tumor response, this agent will be considered negative and no further study would be warranted.

Interim Analysis Decision Rule: Enter 20 evaluable patients. If 2 or more of these 20 evaluable patients have a confirmed tumor response, the study will continue to full accrual. Otherwise, if fewer than 2 confirmed responses are observed, the study will be stopped early and the treatment will be considered ineffective in this patient population. Accrual will continue through the interim analysis phase, unless undue toxicity is observed.

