13.1.5 Power and Significance Level

This design has 90% power to detect a true confirmed response rate of 20%, with a significance level of 0.09 if the true confirmed response rate is 5%. The likelihood of stopping at stage 1 of enrollment is 64.5% and 7% if the true confirmed response rate is 5% and 20%, respectively.

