13.4.6 Laboratory Correlative Studies

All analyses with respect to the translational component of this study are intended to be hypothesis-generating and descriptive in manner. For this study, we will investigate the effect of nivolumab on tumor burden by analyzing the clearance of plasma Epstein-Barr virus (EBV) DNA during the first 4-6 weeks of treatment. In addition, we will investigate the association between treatment outcome and the following immunological markers: Intratumoral expression of PD-1 and PD-L1 in archived NPC tissues, serum absolute lymphocyte count at baseline and post-treatment, expression of PD-1 in CD8+ T cells in tumor infiltrating lymphocytes (TIL) at baseline. Plasma EBV DNA half-life during the first 6 weeks of treatment will be correlated with RECIST-response to nivolumab.

The Chi-Square (or Fisher's Exact test) will be used to assess the association of categorical clinical data with categorical biomarker data. Time-to-event clinical data (PFS, OS) will be correlated with biomarker data using Kaplan-Meier methodology and Cox regression models. Logistic regression models will also be used to predict binary clinical data with baseline biomarker data. Finally, graphical methods and descriptive statistics will be used to summarize the data as well. Two-sided p-values < 0.05 will be considered statistically significant. For the functional MRI parameters, graphical methods and descriptive statistics will be used to assess the changes in these parameters over time. In addition, we will determine the associations between the MRI parameters and clinical endpoints like response and survival.

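### Section 13.4.6 plans logistic regression of response on baseline markers with about 4 to 7 responders and names no sparse-data method: a minor gap, cheaply closed

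*Combined protocol and SAP*

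**What the plan says.** Section 13.4.6 lists the methods for relating markers to outcome. Categorical marker against categorical outcome goes to chi-square or Fisher's exact test, with no rule for choosing between them. Then: "Logistic regression models will also be used to predict binary clinical data with baseline biomarker data". No estimator, interval type, limit on predictors or handling of empty cells is given. The section calls all translational analyses hypothesis-generating, yet also sets two-sided p below 0.05 as statistically significant.

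Section 13.3 treats PD-L1 as positive or negative. Section 9.1.2 has baseline absolute lymphocyte count, a continuous marker, correlated with response.

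Section 2.4 reports that "15/20 NPC tumors (75%) expressed PD-L1" in the investigators' pilot and states an intention to validate the marker. It also cites a head and neck study of another PD-1 inhibitor, in which patients whose tumours overexpressed PD-L1 "had higher tumor response rate (45.5%) than those who did not (11.4"%).

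On size, the design in section 13.1.3 "requires a maximum of 35 evaluable patients, and simultaneously discriminates between tumor response rates of 5% vs. 20"%. The success rule in section 13.1.4 begins "If at least 4 patients have a confirmed tumor response (at least 11%) among the 35 evaluable patients".

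**The concern.** Logistic regression is normally fitted by maximum likelihood. With so few responders that causes two problems. If one marker group has no responders, the likelihood has no finite maximum: software reports a huge coefficient with a huge standard error. For a continuous marker the estimate usually exists, but at this number of events it is too far from the null on average.

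The first problem becomes more likely as the marker becomes more predictive, so the analysis is most fragile where the investigators would most want an effect size. At stake is the usability of the correlative odds ratios (objective 1.3.2), not the trial's main conclusion.

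**Working it through.** **The plan's own figures.** Section 13.1.5 states: "This design has 90% power to detect a true confirmed response rate of 20%, with a significance level of 0.09". Continuing with at least 2 responders in 20 and succeeding with at least 4 in 35, the exact two-stage binomial sum gives power 0.901 at 20%, which reproduces. Type I error is 0.080 with the interim look and 0.096 without it, against 0.09 stated. The probability of stopping at 5% is 0.736, against 64.5% stated; that mismatch is a separate matter and does not enter below. The documents give no separation probability or precision for the marker models.

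**Inputs.**
- 35 evaluable patients (13.1.3).
- Responders: 4 at the boundary (13.1.4); 35 × 0.20 = 7 at the target.
- PD-L1 positive: 15/20 = 75% (2.4), so about 26 positive and 9 negative.
- Association, where one is assumed: 45.5% against 11.4% (2.4), a ratio of 4.0 and an odds ratio of 6.5.

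**Chance that no PD-L1-negative patient responds, at 20% overall response.**
- No association: 0.80^9 = 0.134.
- 4:1 ratio: solve 0.75 × 4x + 0.25 × x = 0.20, so x = 0.20/3.25 = 0.0615 in negatives and 0.246 in positives. Then (1 − 0.0615)^9 = 0.56.

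**Given the number of responders R, no association, 26/9 split.** The probability is C(26,R)/C(35,R): 0.286 for R = 4 and 0.098 for R = 7.

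**Sensitivity.**

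| Assumption | Chance of an empty responder cell |
|---|---|
| No association, 24/11 split, R = 7 | 5.1% |
| No association, 26/9 split, R = 4 | 28.6% |
| No association, 50% positive, R = 7: 2 × 0.5^7 | 1.6% |
| Odds ratio 6.5, 75% positive, 11.4% overall, R = 4: 94.5% of responders are positive, 0.945^4 | 80% |

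**What each method returns when the cell is empty.** Firth's estimate for a 2x2 table adds 0.5 to each cell.

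| | 4/26 v 0/9 | 7/26 v 0/9 |
|---|---|---|
| Maximum-likelihood log odds ratio (SE), as printed | about 21 (16,000) | about 22 (16,000) |
| Wald p | 0.999 | 0.999 |
| Likelihood-ratio p | 0.11 | 0.03 |
| Fisher's exact p | 0.55 | 0.15 |
| Firth odds ratio | (4.5 × 9.5)/(22.5 × 0.5) = 3.8 | (7.5 × 9.5)/(19.5 × 0.5) = 7.3 |
| Firth profile 95% interval | about 0.35 to over 500 | about 0.75 to over 900 |
| Firth p | 0.32 | 0.10 |

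In the right-hand column, whether p falls below 0.05 depends on a choice that section 13.4.6 leaves open.

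**Chi-square or Fisher.** Expected responders among the 9 negatives are 4 × 9/35 = 1.0 to 7 × 9/35 = 1.8, well below the usual minimum of 5 for chi-square.

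**Continuous marker.** This was simulated with 35 patients, about 20% response, at least 4 responders and an assumed true odds ratio of 2 per standard deviation (log odds ratio 0.69). Maximum likelihood averaged 0.83 with root-mean-square error 0.67; Firth averaged 0.71 with 0.53. A repeat run gave 0.82 and 0.70. With three predictors in the model, maximum likelihood averaged 0.94 and Firth 0.70.

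**The case against.** The best reply is that the binary PD-L1 question is already covered. PD-L1 by response is a 2x2 table, Fisher's exact test is named for such tables, and it stays valid with an empty cell. That stands for the p-value. It does not supply an effect size, since the sample odds ratio is still infinite, and it does not apply to lymphocyte count unless that is dichotomised.

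Second, a reader might infer that the plan commits to an unusable Wald test of a leading PD-L1 model. It does not. Section 13.4.6 specifies no Wald test and ranks no marker first. A likelihood-ratio test from the same fit remains usable, as the 0.11 and 0.03 above show.

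Third, the inputs are soft. The 75% rests on 20 tumours. Section 9.1.1.1 defines positivity as staining in tumour cells and in infiltrating lymphocytes; Appendix B (items A4 and C2) requires only one or the other. On-trial prevalence could differ, and every separation figure moves with it. The documents also disagree about the association: section 2.4 says it was not seen in a nivolumab-ipilimumab melanoma study, and section 2.2.7 reports responses in 6 of 13 PD-L1-positive and 9 of 22 negative patients in one regimen, against 4 of 8 and 1 of 13 in the other. All of this stands, which is why a range is given.

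Fourth, the remedy adds no information. About nine negatives carry little, and Firth's intervals show it. That is also true, but a finite estimate with an honestly wide interval is more useful than an infinite one, and for continuous markers the gain in bias and error is real.

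Last, the analyses are exploratory. That lowers the priority, though the 0.05 threshold in the same section invites readers to treat the p-values as findings.

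**Conclusion.** The point holds as a minor improvement. As written, section 13.4.6 can produce an infinite PD-L1 odds ratio and, under maximum likelihood, inflated odds ratios for continuous markers.

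The 13% and 56% are two scenarios, not the ends of one probability. Both assume 26 positive, 9 negative and 20% overall response; the first assumes no association, and the second borrows a ratio from another drug and tumour. A reader might take them as a forecast of how often the PD-L1 analysis will fail. The documents do not support that, because prevalence and association are both unknown; about 5% to 80% is the fairer statement, and lower still at 50% prevalence.

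Nor is 4 to 7 a bound on responders. A trial stopped at the interim would have 0 or 1 in its first 20 patients, and a response rate above 20% would give more and make separation rarer: at 30% with no association, 0.70^9 = 4%.

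The size of the bias for continuous markers rests on the assumed odds ratio of 2 per standard deviation. No eligibility, stopping or primary-endpoint decision depends on any of this.

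**What to change.** In section 13.4.6:
- Specify Firth penalised-likelihood logistic regression for binary outcomes, one marker per model, with profile-likelihood 95% confidence intervals.
- Make Fisher's exact test, not chi-square, the default for 2x2 tables.
- Reconcile the PD-L1 positivity definition between section 9.1.1.1 and Appendix B, so that the groups being compared are fixed.

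Settle the wording before response is tabulated by marker, so that the method is not chosen after an empty cell appears.

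The cost is a few sentences; the methods are in standard software, and no extra patients or data are needed. The downside is that estimates shrink towards 1, substantially where a cell is empty (from infinity to 3.8 or 7.3 in the examples), and intervals will still be very wide.

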13.5 Adverse Event Stopping Rule

13.5.1 Monitoring

The principal investigator and the study statistician will review the study periodically (every 4-6 months, or more frequently if clinically indicated) to identify accrual, toxicity, and any endpoint problems that might be developing.

13.5.2 Adverse Event Stopping Rule

Based on prior studies using nivolumab at the dose and schedule to be used in this study, we expect approximately 10% of patients to experience grade 4+ adverse events (at least possibly related to study medication). In this study, we will suspend accrual to allow for a full review of the data, if any of the following occur:

- (1) If at any time, 4 of the initial 20 patients (or 20% of all patients when accrual is greater than 20) have experienced any grade 4 adverse event (at least possibly related to the study medication).
- (2) If at any time, 2 of the initial 20 patients (or 10% of all patients when accrual is greater than 20) have experienced any grade 5 adverse event (at least possibly related to the study medication). Of course, we will also closely monitor each grade 5 event on a case-by-case basis, and may immediately suspend accrual after one grade 5 event if we feel it is best for patient safety.

After consideration by the study team [ie, Study Chair(s), Statistician, P2C Operations Office, etc] and consultation with representatives at the Cancer Therapy Evaluation Program (CTEP) and the NCI Central IRB (CIRB) , a decision will be made as to whether and how the study will proceed.

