13.2 Sample Size/Accrual Rate

13.2.1 Sample Size

A total of 35 evaluable patients will be accrued per study design, unless the study is permanently closed at interim analysis or undue toxicity is observed. We anticipate accruing an additional 5 patients in order to account for ineligibility, cancellation, major treatment violation, or other reasons. Therefore, maximum accrual is 40 patients for this trial.

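### The toxicity rule's benchmark is for grade 4+ events, but its two triggers count grade 4 and grade 5 patients separately, so 3 grade 4 plus 1 grade 5 among the first 20 patients meets neither

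*Combined protocol and SAP*

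**What the plan says.** Section 13.5.2 opens with the benchmark: "we expect approximately 10% of patients to experience grade 4+ adverse events (at least possibly related to study medication"). It then sets two conditions, either of which suspends accrual for a full review of the data.

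- Condition (1) has the threshold "4 of the initial 20 patients (or 20% of all patients when accrual is greater than 20"). The patients counted towards it are those who "have experienced any grade 4 adverse event (at least possibly related to the study medication").
- Condition (2) has the threshold "2 of the initial 20 patients (or 10% of all patients when accrual is greater than 20"). The patients counted towards it are those who "have experienced any grade 5 adverse event (at least possibly related to the study medication").

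The section also commits the team to close monitoring of each grade 5 event, and says that it "may immediately suspend accrual after one grade 5 event if we feel it is best for patient safety". No sentence says that a grade 5 patient also counts in condition (1), and no condition counts grades 4 and 5 together. Section 13.2.1 states that "maximum accrual is 40 patients for this trial". The plan gives no trigger probabilities for this rule.

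**The concern.** The expected rate is for grade 4 and grade 5 combined, but the rule monitors the two grades apart. Toxicity divided between them can therefore reach twice the expected combined rate without a mandatory pause. In one configuration, replacing a grade 4 event by a death turns a trigger into a non-trigger.

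This matters because Section 13.5.2 holds the only numerical trial-level toxicity trigger. Section 13.5.1 schedules review every 4 to 6 months, and Section 13.2.2 expects about 2 patients per month. Between scheduled reviews, 2 × 4 = 8 to 2 × 6 = 12 more patients may enter. What would be lost is a timely mandatory review.

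**Working it through.** **Inputs.** From Section 13.5.2: benchmark 10% grade 4+; thresholds 4 and 2 in the first 20 patients, then 20% and 10%. From Section 13.2.1: at most 40 patients. Assumed, because the documents do not give it: the fatal share of grade 4+ events. Each patient is classed by worst related grade. After 20 patients, a threshold is the smallest whole number at or above the stated percentage.

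**Internal check.** 4/20 = 20% and 2/20 = 10%, so the counts and percentages agree. There is no stated operating characteristic to reproduce.

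**Step 1: all splits of four affected patients among 20.**

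| Grade 4 | Grade 5 | Condition (1), needs 4 | Condition (2), needs 2 | Pause |
|---|---|---|---|---|
| 4 | 0 | met | not met | yes |
| 3 | 1 | not met | not met | **no** |
| 2 | 2 | not met | met | yes |
| 1 | 3 | not met | met | yes |
| 0 | 4 | not met | met | yes |

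**Step 2: later accrual.** The largest grade 4+ count that meets neither condition is (threshold 1 − 1) + (threshold 2 − 1). If condition (1) counted grade 4 or higher, the largest count would be threshold 1 − 1.

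| Patients | Thresholds | Largest count, as written | Largest count, grade 4+ in (1) |
|---|---|---|---|
| 25 | 5 and 3 | 4 + 2 = 6 (24%) | 4 |
| 30 | 6 and 3 | 5 + 2 = 7 (23%) | 5 |
| 35 | 7 and 4 | 6 + 3 = 9 (26%) | 6 |
| 40 | 8 and 4 | 7 + 3 = 10 (25%) | 7 |

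**Step 3: probability of the gap at 20 patients.** With per-patient probabilities p4 and p5 (worst grade 4, worst grade 5):

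P(3 + 1) = 20!/(3! 1! 16!) × p4³ × p5 × (1 − p4 − p5)¹⁶, where the coefficient is 1140 × 17 = 19,380.

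- True rate 10%, one tenth fatal: 19,380 × 0.09³ × 0.01 × 0.9¹⁶ = 0.026.
- True rate 20%, one tenth fatal: 19,380 × 0.18³ × 0.02 × 0.8¹⁶ = 0.064.

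For fatal shares from 10% to 30% the range is 0.026 to 0.037 at a true 10%, and 0.064 to 0.090 at a true 20%. At 20 patients this probability is exactly the difference between the two versions of the rule. At 18% + 2%, for example, the trigger probability is 0.532 as written and 0.596 with grade 4 or higher in condition (1).

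**Step 4: probability of triggering at any time up to 40 patients.** This is an exact patient-by-patient recursion on the two counts, checking both thresholds after each patient.

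| True grade 4 + grade 5 | As written | Grade 4+ in (1) | Difference (points) |
|---|---|---|---|
| 19.5% + 0.5% | 71.6% | 73.8% | 2 |
| 18% + 2% | 66.5% | 74.2% | 8 |
| 15% + 5% | 64.5% | 76.6% | 12 |
| 10% + 10% | 78.7% | 84.6% | 6 |
| 5% + 15% | 93.0% | 93.6% | 1 |
| 9% + 1% (expected total) | 14.0% | 17.6% | 4 |
| 8% + 2% (expected total) | 14.8% | 20.0% | 5 |

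**Step 5: sensitivity.** A patient who died and also had a separate related grade 4 event already counts in condition (1). If half of the fatal cases at 15% + 5% are like this, the comparison is 70.6% against 76.6%, so the difference halves to 6 points. With no fatal events the two versions are identical.

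**The case against.** Separate limits for life-threatening and fatal events are a legitimate design. The 10% figure is offered as an expectation, and nothing says that condition (1) must test the combined rate. Every configuration missed contains at least one related death, and the plan does not ignore deaths: monitoring of each one is committed, and only suspension is optional. Section 7.3.3 requires 24-hour reporting of serious grade 3 to 5 events. Sections 13.1.4, 13.1.7, 13.2.1 and 14.1 also allow stopping or closure for toxicity. A trigger only pauses accrual for review. The probabilities above give these safeguards no weight, so they are upper bounds on the practical loss.

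Most of this stands and limits the size of the point. It does not close the gap. The other stopping provisions carry no number, several depend on agreement between CTEP and the investigators, and the stopping criteria that Section 14.1 cites in Section 5.3 concern individual patients.

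A reader might infer four stronger things that the documents do not support.

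- *Any four grade 4+ events in 20 patients can escape.* The rule counts patients, and only the 3 + 1 split escapes.
- *The rule as a whole treats a death as less serious.* A death has its own condition, at half the threshold.
- *This is the only safety boundary.* It is the only numerical one at trial level.
- *The gap is widest when most toxicity is fatal.* It shrinks to about 1 point at 5% + 15%, because condition (2) then takes over.

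The 12-point figure needs a 5% related-death rate, which the documents do not suggest. Section 2.2.6 mentions 3 deaths from pulmonary toxicity beside a denominator of 296. If that is the right denominator, 3/296 is about 1%.

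**Conclusion.** The mismatch is real on the text, and its practical effect is modest. A literal reading leaves one configuration at 20 patients, 3 grade 4 plus 1 grade 5, that reaches twice the benchmark without a mandatory pause. At later accrual, grade 4+ rates of 23% to 26% can meet neither condition at the sizes tabulated.

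At a true 20% grade 4+ rate, the loss in trigger probability over 40 patients is about 2 points at 0.5% fatal, 8 at 2% and 12 at 5%. These figures assume worst-grade classification, immediate counting of events in order of entry, and no separate related grade 4 event in patients who die. If such events occur, the loss is smaller. If the sponsor already intends grade 5 patients to count in condition (1), the wording should still say so. The change is worth making because it aligns trigger and benchmark at little cost.

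**What to change.** In condition (1) of Section 13.5.2, count patients with a related adverse event of *grade 4 or higher* instead of grade 4. Leave condition (2) and the single-death clause unchanged.

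The cost is a short protocol wording change and more unnecessary pauses. At the expected 10% rate, the chance of a pause over 40 patients rises from 14.0% to 17.6% (9% + 1%) or from 14.8% to 20.0% (8% + 2%), about 4 to 5 points. A pause leads to a data review and does not by itself end the trial.

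If the sponsor prefers to keep the grades separate, the section should give an expected rate for each grade and state that no combined limit applies. That would remove the inconsistency but leave the gap.
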